8.8 Unscheduled Visits

No unscheduled visits are defined for this study.

8.9 Software Version

All statistical analyses will be conducted using SAS® (SAS Institute, North Carolina), version 9.4.

Document:	\	.net\Enterprise\Sites\USCBG\Depts\BioStat\Boehringer\Documentation\SAP\Final
Author:		Version Number: 1.0

Template No.: RWI_TP_BIOS0013 Revision 1 Reference: RWI_WI_BIOS0015

Effective Date: 15Jun2018

9. STATISTICAL CONSIDERATIONS

9.1 Statistical Tests and Confidence Intervals

Unless otherwise specified in the description of the analyses, all statistical tests will be two-sided and performed considering a significance level of 0.05. All statistical tests are exploratory due to the nature of the study, therefore no adjustment for multiplicity is considered in this SAP.

Whenever applicable, two-sided 95% CIs for proportions calculated using the exact Binomial (Clopper-Pearson) method [3] and 95% CIs of a normal distribution for means will be provided.

The normality assumption of the distributions of continuous variables will be tested using the Kolmogorov-Smirnov test (if $n \geq 50$) or Shapiro Wilk test (if $n < 50$). In addition, the visualisation of data distribution (skewness and kurtosis) may be performed using histograms/box-plot. Non-parametric tests will be used whenever the normality assumption is not accepted.

9.2 Rules for Reporting Statistics

Continuous variables will be summarised using descriptive statistics, i.e., number of non-missing and missing observations, mean, SD, first quartile (Q1), median, third quartile (Q3), minimum and maximum. Whenever applicable, two-sided 95% CIs will be calculated for the difference of means.

For reporting conventions:

- The number of non-missing and missing observations will be presented as whole numbers.

Document: \\\\ .net\\Enterprise\\Sites\\USCBG\\Depts\\BioStat\\Boehringer\\Documentation\\SAP\\Final

Author: _____ Version Number: _____

10

Version Date:

100CT2019

Template No.: RWI_TP_BIOS0013 Revision 1

Reference: RWI WI BIOS0015

Effective Date: 15-Jun-2018

- The minimum and maximum will be presented with the same number of decimal places as in the raw data.
- The mean, median, Q1 and Q3 will generally be displayed with one more decimal place than the raw data.
- The SD will generally be displayed with two more decimal places than the raw data. If there is only one observation (n=1), the SD will be displayed as a hyphen ("--"). If there is no observation, summary statistics will be displayed with a hyphen ("--").

Qualitative variables will be summarised by frequency counts (n) and percentages (%). Percentages will not include the missing category and are calculated over the number of patients with available (non-missing) data. Counts of missing data will be provided in the tables for information only. Wherever applicable, 95% CIs will also be presented.

For reporting conventions, percentages will be reported to one decimal place unless greater precision is deemed appropriate, except for cases when 100% is presented. In cases of a count of 0, the percentage will not be presented.

P-values will be rounded to three decimal places. P-values rounded to less than 0.001 will be reported as <0.001 in tables. P-values greater than 0.999 will be reported as >0.999.

9.3 Missing Data

Due to the nature of the study, there will likely be missing data (data that are not collected or documented in the patient medical record).

Document:	\	.net\Enterprise\Sites\USCBG\Depts\BioStat\Boehringer\Documentation\SAP\Final
Author:		Version Number: 1.0

Template No.: RWI_TP_BIOS0013 Revision 1 Reference: RWI_WI_BIOS0015

Effective Date: 15Jun2018

Unless otherwise specified in this SAP, all data will be evaluated as reported and no imputation for missing values will be done, except for dates and PASAPQ data. Handling of partial dates and PASAPQ data is described in [Appendix 2](#) and [Section 20.1.2](#), respectively.

Missingness for all variables will be indicated in descriptive tables. In all listings, imputed values will not be presented, however, all variables derived based on imputed values will be flagged.

9.4 Examination of Subgroups

Subgroup analyses (in case of more than 20% of patients included in the FAS) will be conducted on primary and secondary outcomes based on the subgroups as defined below (some categories may be grouped when needed). The subgroup analyses will not be performed on any subgroup category “Missing”, “Unknown”, “None” or “Not Assessed”. All the subgroup analyses will be exploratory.

The following subgroups will be defined:

- Age:
 - ≥ 40 to < 65 years.
 - ≥ 65 to < 75 years.
 - ≥ 75 years.
- Global Initiative for Chronic Obstructive Lung Disease (GOLD) patient group:
 - A (less symptoms / low risk).
 - B (more symptoms / low risk).
 - C (less symptoms / higher risk).
 - D (more symptoms / higher risk).

Document: \\ .net\Enterprise\Sites\USCBG\Depts\BioStat\Boehringer\Documentation\SAP\Final

Author: Version Number: 1.0
Version Date: 100CT2019

Template No.: RWI_TP_BIOS0013 Revision 1

Reference: RWI_WI_BIOS0015

Effective Date: 15Jun2018

- GOLD grade:
 - 1 (Mild).
 - 2 (Moderate).
 - 3 (Severe).
 - 4 (Very Severe).
- Smoking status:
 - Current.
 - Former.
 - Never.
- Type of re-usable Respimat® SMI product prescribed at study entry:
 - Spiriva® 2.5 µg inhalation solution.
 - Striverdi® 2.5 µg inhalation solution.
 - Spiolto® 2.5 µg / 2.5 µg inhalation solution.
- For Respimat® SMI-naïve patients, last non-Respimat® SMI maintenance product prescribed prior to study entry: refer to “Medication” column in [Table 4](#).
- For Respimat® SMI-naïve patients, last inhaler device used prior to study entry:
 - Dry powder inhaler (DPI).
 - Metered dose inhaler (MDI).

10. OUTPUT PRESENTATIONS

A separate document displays the format, layout and content of the TLFs shells to be provided by RWS Biostatistics.

Document: \\ .net\Enterprise\Sites\USCBG\Depts\BioStat\Boehringer\Documentation\SAP\Final
Author: Version Number: 1.0
Version Date: 100CT2019

Template No.: RWI_TP_BIOS0013 Revision 1

Reference: RWI WI BIOS0015

Effective Date: 15Jun2018

11. PATIENT DISPOSITION

The following data related to patient disposition will be summarised by patient cohort and overall:

- Number of enrolled patients.
- Number (%) of eligible patients.
 - Study duration (days) - calculated relative to date of signed ICF.
- Number (%) of non-eligible patients.
 - Reason for ineligibility: inclusion criteria not met, exclusion criteria not met.
- Number (%) of patients included in FAS.
 - By visit: Baseline visit, Follow-up assessment.
 - Re-usable Respimat® SMI product prescribed at study entry: Spiriva® 2.5 µg inhalation solution, Striverdi® 2.5 µg inhalation solution, Spiolto® 2.5 µg / 2.5 µg inhalation solution.
 - For Respimat® SMI-experienced patients, Respimat® SMI product prescribed prior to study entry: Disposable/Re-usable Spiriva® 2.5 µg inhalation solution, Disposable/Re-usable Striverdi® 2.5 µg inhalation solution, Disposable/Re-usable Spiolto® 2.5 µg / 2.5 µg inhalation solution.
 - Number (%) of patients with any non-Respimat® SMI maintenance product prescribed prior to study entry.
- Number (%) of patients who completed the study.
 - Study duration (days) - calculated relative to date of signed ICF.
- Number (%) of patients who discontinued the study.

Document: \\ .net\Enterprise\Sites\USCBG\Depts\BioStat\Boehringer\Documentation\SAP\Final

Author: Version Number: 1.0
Version Date: 100CT2019

Template No.: RWI_TP_BIOS0013 Revision 1

Reference: RWI_WI_BIOS0015

Effective Date: 15Jun2018

- Reason for study discontinuation: Adverse event, Death, Lost to follow-up, Compliance, Study terminated by sponsor, Withdrawal by patient, Other.
- Study duration (days) - calculated relative to date of signed ICF.

Derivations:

- *Study duration (days) = (End of study date – date of signed ICF + 1).*

Supportive listings for patient disposition will be provided.

12. DEMOGRAPHIC AND OTHER BASELINE CHARACTERISTICS

12.1 Demographics

Analysis Set: FAS

Demographic characteristics will be summarised with descriptive statistics by patient cohort and overall using the information collected from the “Demographics” eCRF page. Demographic characteristics will include:

- Age (years) - calculated relative to year of signed ICF.
 - Age categories: ≥ 40 to < 65 years, ≥ 65 to < 75 years, ≥ 75 years.
- Gender: Male, Female.
- Ethnicity: Hispanic or Latino, Not Hispanic or Latino, Not reported, Unknown.

- Race: American Indian or Alaska Native, Black or African American, Asian, Native Hawaiian or other Pacific Islander, White, Unknown, Not reported, Not applicable – not collected per local regulations, Other.
Note: An additional category “Mixed” will be created for patients with more than one race reported.
- Education level: Elementary school, High school, University degree.
- Years of education: No formal education, 1-9 years, 10-12 years, 13-15 years, 16 years or more.

Derivations:

- $Age \text{ (years)} = (year \text{ of signed ICF} - year \text{ of birth})$.

12.2 Disease History

Analysis Set: FAS

Disease history will be summarised with descriptive statistics by patient cohort and overall.

The date of COPD diagnosis will be collected from the “Previous COPD History and Exacerbations” eCRF page and will be used to derive age at COPD diagnosis (years) and COPD duration (years):

- Age at COPD diagnosis (years) - calculated relative to year of COPD diagnosis.
- COPD duration (years) - calculated relative to signed ICF date.

Document:	\	.net\Enterprise\Sites\USCBG\Depts\BioStat\Boehringer\Documentation\SAP\Final
Author:		Version Number: 1.0

Template No.: RWI_TP_BIOS0013 Revision 1

Reference: RWI_WI_BIOS0015

Effective Date: 15Jun2018

Derivations:

- *Age at COPD diagnosis (years) = (year of COPD diagnosis – year of birth).*
- *COPD duration (years) = Integer part of [(date of signed ICF – date of COPD diagnosis) + 1] / 365.25.*

Details on conversion factors used for dates and handling of partial date of COPD diagnosis are described in [Appendix 1](#) and [Appendix 2](#), respectively.

12.3 Vital Signs

Analysis Set: FAS

Vital signs will be summarised with descriptive statistics by patient cohort and overall using the information collected from the “Vital Signs” eCRF page. Vital signs data will include the following:

- Weight (kg).
- Height (cm).
- Body mass index (BMI) [kg/m²] - calculated relative to baseline weight and height.
 - BMI categories: Underweight (<18.5 kg/m²), Normal (≥18.5 to <25.0 kg/m²), Overweight (≥25.0 to <30.0 kg/m²), Obese (≥30.0 kg/m²).
- Systolic blood pressure (SBP) [mmHg].
 - SBP categories: <120 mmHg, ≥120 to <140 mmHg, ≥140 to <160 mmHg, ≥160 mmHg.
- Diastolic blood pressure (DBP) [mmHg].

Document: \\ .net\Enterprise\Sites\USCBG\Depts\BioStat\Boehringer\Documentation\SAP\Final

Author: Version Number: 1.0
Version Date: 100CT2019

Template No.: RWI_TP_BIOS0013 Revision 1

Reference: RWI_WI_BIOS0015

Effective Date: 15Jun2018

- DBP categories: <80 mmHg, ≥ 80 to <90 mmHg, ≥ 90 to <100 mmHg, ≥ 100 mmHg.

Derivations:

- $BMI \text{ (kg/m}^2\text{)} = \text{Weight (kg)} / [\text{Height (cm)} / 100]^2$.

Height and weight measurements will be converted according to the conversion factors described in [Appendix 1](#).

12.4 COPD Symptom Severity Assessments

Analysis Set: FAS

The COPD Assessment Test (CAT), the Modified Medical Research Council Scale (mMRC) and the GOLD Classifications will be used to assess the presence and magnitude of respiratory symptoms. Data on respiratory symptoms severity will be summarised with descriptive statistics using the information collected from the “COPD Symptom Severity Assessment” eCRF page.

- CAT score.
 - CAT score categories: Low impact (≥ 0 to <10), Medium impact (≥ 10 to <20), High impact (≥ 20 to <30), and Very high impact (≥ 30 to ≤ 40).
- mMRC score: Grade 0, Grade 1, Grade 2, Grade 3, Grade 4, Unknown.
- GOLD grade: 1 (Mild), 2 (Moderate), 3 (Severe), 4 (Very Severe), Not assessed.
- Patient group: A (less symptoms / low risk), B (more symptoms / low risk), C (less symptoms / higher risk), D (more symptoms / higher risk), Not assessed.

Document: \\ .net\Enterprise\Sites\USCBG\Depts\BioStat\Boehringer\Documentation\SAP\Final

Author: Version Number:

1.0

Version Date:

100CT2019

Template No.: RWI_TP BIOS0013 Revision 1

Reference: RWI WI BIOS0015

Effective Date: 15-Jun-2018

12.5 Spirometry

Last pre-bronchodilator and post-bronchodilator spirometry measurements available in the 12-month period prior to study entry will be summarised with descriptive statistics using the information collected from the “Post-Bronchodilator Spirometry Measurement” eCRF page. Spirometry data will include:

- Time since last available spirometry assessment (months) - calculated relative to signed ICF date.
- Forced vital capacity (FVC) (L).
- Forced expiratory volume (FEV₁) (L).
- FEV₁/FVC ratio (%).
 - FEV₁/FVC ratio (%) categories: <70%, ≥70%.
- FVC predicted (L) – calculated based on European Coal and Steel Community (ECSC) equations [\[4\]](#).
- FEV₁ predicted (L) – calculated based on ECSC equations [\[4\]](#).
- FVC predicted (%).
- FEV₁ predicted (%).

Derivations:

- *Time since last available spirometry assessment (months) = [(date of signed ICF – date of last available spirometry assessment) + 1] / 30.4375.*
- *FVC predicted (L):*

Document:	\	.net\Enterprise\Sites\USCBG\Depts\BioStat\Boehringer\Documentation\SAP\Final
Author:		Version Number: 1.0

Template No.: RWI_TP_BIOS0013 Revision 1

Reference: RWI_WI_BIOS0015

Effective Date: 15Jun2018

- *Males: $FVC_{predicted}(L) = 0.0576 * (Height [cm]) - 0.026 * Age (years) - 4.34$, where $Age (years) = (year of last available spirometry assessment - year of birth)$ and $Height (cm) = Height (cm)$ collected from the “Vital Signs” eCRF page.*
- *Females: $FVC_{predicted}(L) = 0.0443 * (Height [cm]) - 0.026 * Age (years) - 2.89$, where $Age (years) = (year of last available spirometry assessment - year of birth)$ and $Height (cm) = Height (cm)$ collected from the “Vital Signs” eCRF page.*
- $FEV_1_{predicted}(L)$:
 - *Males: $FEV_1_{predicted}(L) = 0.043 * (Height [cm]) - 0.029 * Age (years) - 2.49$, where $Age (years) = (year of last available spirometry assessment - year of birth)$ and $Height (cm) = Height (cm)$ collected from the “Vital Signs” eCRF page.*
 - *Females: $FEV_1_{predicted}(L) = 0.0395 * (Height [cm]) - 0.025 * Age (years) - 2.60$, where $Age (years) = (year of last available spirometry assessment - year of birth)$ and $Height (cm) = Height (cm)$ collected from the “Vital Signs” eCRF page.*
- $FVC_{predicted} (\%) = [FVC(L) / FVC_{predicted}(L)] * 100$.
- $FEV_1_{predicted} (\%) = [FEV_1(L) / FEV_1_{predicted}(L)] * 100$.

Details on conversion factors used for dates and handling of partial date of last available spirometry assessment prior to study entry are described in [Appendix 1](#) and [Appendix 2](#), respectively.

Supportive listings for demographic and other baseline characteristics will be provided.

Document:	\\ .net\Enterprise\Sites\USCBG\Depts\BioStat\Boehringer\Documentation\SAP\Final	
Author:	Version Number:	1.0

Template No.: RWI_TP_BIOS0013 Revision 1

Reference: RWI_WI_BIOS0015

Effective Date: 15Jun2018

13. SMOKING STATUS

Analysis Set: FAS

Smoking status at baseline and at follow-up assessment will be summarised with descriptive statistics by patient cohort and overall using the following information collected from the correspondent “Smoking Status” eCRF pages.

At Baseline Visit:

- Smoking status: Current smoker, Former smoker, Never smoked.
- Number of pack-years (one pack-year = one pack of 20 cigarettes per day for a year).
 - Number of pack-years categories: <10 pack-years, ≥ 10 pack-years.

At Follow-up Assessment:

- Any change in smoking status?: Yes, No.
- Change status: Started, Stopped.

Derivations:

- *Number of packs = (Number of cigarettes/20).*

Details on conversion factors used for number of cigarettes are described in [Appendix 1](#).

Supportive listings for smoking status at baseline and at follow-up assessment will be provided.

Document:	\	.net\Enterprise\Sites\USCBG\Depts\BioStat\Boehringer\Documentation\SAP\Final	
Author:		Version Number:	1.0

Template No.: RWI_TP_BIOS0013 Revision 1

Reference: RWI_WI_BIOS0015

Effective Date: 15Jun2018

14. PREVIOUS AND CONCURRENT COPD EXACERBATIONS

Analysis Set: FAS

Previous (in the 12 months prior to study entry) and concurrent COPD exacerbations (after the study entry, during the study period) will be summarised by patient cohort and overall from the “Previous/Concurrent COPD Exacerbations” and “Previous/Concurrent COPD Exacerbations Details” eCRF pages. Summaries of previous and concurrent COPD exacerbations will include:

- Any COPD exacerbation?: Yes, No.
- Number of COPD exacerbations (per patient).
 - Number of COPD exacerbations (per patient) categories: 0, 1, ≥ 2 .

Supportive listing for previous and concurrent exacerbations will be provided.

15. COMORBIDITIES

Analysis Set: FAS

Comorbidities other than COPD reported during the study period will be coded using the most current available version of Medical Dictionary for Regulatory Activities (MedDRA) at the time of DBL and will be analysed overall and by patient cohort from the “Comorbidities”/“Comorbidities Details” eCRF pages.

Comorbidities will be summarised as the number and percentage of patients by MedDRA preferred term (PT) as an event category and MedDRA primary system organ class (SOC) as a summary category. Each patient will be counted only once within a given SOC and PT.

Document: \\\\ .net\\Enterprise\\Sites\\USCBG\\Depts\\BioStat\\Boehringer\\Documentation\\SAP\\Final

Author: Version Number:

1.0

Version Date:

100CT2019

Template No.: RWI TP BIOS0013 Revision 1

Reference: RWI WI BIOS0015

Effective Date: 15Jun2018

Comorbidities will be displayed in terms of frequency tables sorted on alphabetical order of SOC and decreasing frequency of PT within a given SOC. In case of equal frequency regarding PT, alphabetical order will be used. In case any specific comorbidity does not have MedDRA SOC coded term, it will be summarised under the “Unavailable MedDRA SOC classification” category.

A supportive listing for comorbidities will be provided.

16. PREVIOUS AND CONCOMITANT MEDICATIONS

Analysis Set: FAS

Concomitant medications are medications which started prior to the study entry (date of signed ICF) and continued during the study period, as well as those that started during the study period. Any medication without the start and end date will also be considered as concomitant. Previous medications are those medications which were started and stopped in the 6 months prior to study entry.

Previous and concomitant medications will be coded using the most current available version of World Health Organization Drug Dictionary (WHO-DD) B3 Format at the time of DBL and will be analysed overall and by patient cohort regarding COPD-related status from the “Prior & Current COPD & Non-COPD Medications”/“Prior & Current COPD & Non-COPD Medications Details” eCRF pages.

Previous and concomitant medications will be summarised as the number and percentage of patients by PT. Each patient will be counted only once within a given PT. Previous and Document: \\ .net\Enterprise\Sites\USCBG\Depts\BioStat\Boehringer\Documentation\SAP\Final

Author: Version Number: 1.0
Version Date: 100CT2019

Template No.: RWI_TP_BIOS0013 Revision 1

Reference: RWI_WI_BIOS0015

Effective Date: 15Jun2018

concomitant medications will be displayed in terms of frequency tables sorted on decreasing frequency of PT. In case of equal frequency regarding PT, alphabetical order will be used.

A supportive listing for previous and concomitant medications taken previously and during the study period will be provided.

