### **9.3.3 Covariates**

The following covariates, where available, will be collected and assessed at study enrolment (baseline visit) and/or study end (follow-up assessment). See [Table 1](#) for the timing of data collection:

- Patient demographics (e.g. age, gender, height, weight, highest level of educational attainment)
- Duration of COPD
- Number of COPD exacerbations, based on medical history, in the 12 months prior to study entry or in the study period
- Pulmonary function (post-bronchodilator expiratory volume in one second [FEV1] and forced vital capacity [FVC]), based on most recent spirometry test in the 12 months prior to study entry (if available)
- COPD Assessment Test (CAT) score or modified Medical Research Council (mMRC) dyspnoea scale (if available)
- COPD severity (grade [1-4] and patient group [A, B, C or D]) based on the 2019 Global Initiative for Chronic Obstructive Lung Disease (GOLD) grade ([GOLD 2019](#))
- Respimat SMI type used during study period (disposable or re-usable)
- Duration of treatment with Respimat SMI (for Respimat SMI-experienced patients) (if available)
- Last day of use of disposable Respimat SMI (for Respimat SMI-experienced patients)
- Date of first prescription of re-usable Respimat SMI
- COPD-related and other concomitant medications, based on medical prescription history, in the 6 months prior to study entry and during the study period
- Comorbidities such as cardiovascular diseases, malignancies (e.g. lung cancer), diabetes mellitus, musculoskeletal diseases, renal diseases, liver diseases, osteoporosis, gastroesophageal reflux, other respiratory diseases (e.g. asthma, pulmonary fibrosis, pneumonia), or mental health conditions (e.g. depression, anxiety)

- Serious and non-serious ADRs, AEs with a fatal outcome, pregnancies and other reportable safety events (as outlined in [Section 10.2](#)) during the study period
- Smoking status/history (current smokers, former smokers, and never smokers) and pack-years (for current smokers)
- Details of discontinuation of the re-usable Respimat SMI during the study period (if applicable)

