18. PREVIOUS NON-RESPIMAT® SMI MAINTENANCE PRODUCT USE

Analysis Set: FAS

Information on previous non-Respimat® maintenance product use in the 6 months prior to study entry will be collected on the “Prior & Current COPD & Non-COPD Medications”/“Prior & Current COPD & Non-COPD Medications Details” eCRF pages.

Non-Respimat® SMI maintenance product is defined as a related COPD inhaler other than Respimat® SMI products which was given for maintenance treatment. Some of non-Respimat® SMI maintenance products that will be considered in this study and the correspondent type of inhaler devices are described in [Table 4](#). Other non-Respimat® SMI maintenance products identified prior to the DBL that are not presented in [Table 4](#) will also be considered in the final analysis.

Document:	\	.net\Enterprise\Sites\USCBG\Depts\BioStat\Boehringer\Documentation\SAP\Final
Author:		Version Number: 1.0

Template No.: RWI_TP_BIOS0013 Revision 1 Reference: RWI_WI_BIOS0015

Effective Date: 15Jun2018

Table 4 Non-Respimat® SMI maintenance products and type of inhaler devices

Medication	Pharmacological class	Inhaler type
Oxeze®/Oxis® Turbuhaler (formoterol)	LABA	DPI
Foradil® Aerolizer (formoterol)	LABA	DPI
Hirobriz®/Onbrez®/Oslif® Breezhaler (indacaterol)	LABA	DPI
Serevent®/Dilamax®/Ultrabeta® Diskus (salmeterol)	LABA	DPI
Atimos® (formoterol)	LABA	MDI
Serevent®/Dilamax®/Salmeterol Neolab®/Ultrabeta® (salmeterol)	LABA	MDI
Seebri®/Tovanor® Breezhaler (glycopyrronium)	LAMA	DPI
Spiriva®/Braltus®/Grgal® Handihaler (tiotropium)	LAMA	DPI
Bretaris®/Eklira® Genuair (aclidinium)	LAMA	DPI
Incruse® Ellipta (umeclidinium)	LAMA	DPI
Anoro®/Laventair® Ellipta (umeclidinium plus vilanterol)	LAMA + LABA	DPI
Brimica®/Duaklir® Genuair (aclidinium plus formoterol)	LAMA + LABA	DPI
Ultibro®/Xoterna® Breezhaler (glycopyrronium plus indacaterol)	LAMA + LABA	DPI
Bevespi® Aerosphere (glycopyrronium plus formoterol)	LAMA + LABA	MDI
Symbicort®/Assieme® Turbuhaler (budesonide plus formoterol)	ICS + LABA	DPI
DuoResp®/BiResp® Spiromax (budesonide plus formoterol)	ICS + LABA	DPI
Bufomix®/Gibiter® Easyhaler (budesonide plus formoterol)	ICS + LABA	DPI
Seretide®/Brisomax®/Maizar®/Veraspir® Diskus (fluticasone propionate plus salmeterol)	ICS + LABA	DPI
Aerivio®/Airexar® Spiromax (fluticasone propionate plus salmeterol)	ICS + LABA	DPI
AirFluSal® ForSpiro (fluticasone propionate plus salmeterol)	ICS + LABA	DPI
Breo®/Relvar®/Revinty® Ellipta (fluticasone furoate plus vilanterol)	ICS + LABA	DPI

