- *Duration of non-Respimat® SMI maintenance product prescribed prior to study entry (days) = [(End date – Start date) + 1].*
- *Last non-Respimat® SMI maintenance product prescribed prior to study entry = non-Respimat® maintenance product prescribed prior to study entry where max (Start date) < date of signed ICF and End date < date of signed ICF.*
- *Last inhaler device used prior to study entry = inhaler device associated with the last non-Respimat® SMI maintenance product prescribed prior to study entry.*

Details on conversion factors used for dates and on handling of partial dates of start and end date of medications are described in [Appendix 1](#) and [Appendix 2](#), respectively.

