23.2 APPENDIX 2. Partial Date Conventions

Partial dates will be imputed as follows:

Previous and Concomitant Medications:

Incomplete dates for previous/concomitant medications will be imputed as follows:

- If the medication start date is missing completely, then the medication date will be replaced by the signed ICF date.
- If the day of medication start date is missing, but the month and year are equal to the signed ICF date, then the medication date will be replaced by the signed ICF date.
- If both the day and month of the medication start date are missing but the year is equal to the signed ICF year, then the medication start date will be replaced by the signed ICF date.
- In all other cases, the missing medication day or missing medication month will be replaced by 1.
- Incomplete medication stop date will be replaced by the last day of the month (if day is missing only), if not resulting in a date later than the date of the subject's death. In the latter case, the date of death will be used to impute the incomplete stop date.
- In all other cases, the incomplete medication stop date will not be imputed.

Disease History and Spirometry:

Incomplete dates for date of COPD diagnosis and date of last available spirometry assessment prior to study entry will be imputed as follows:

Document:	\	.net\Enterprise\Sites\USCBG\Depts\BioStat\Boehringer\Documentation\SAP\Final	
Author:		Version Number:	1.0

Template No.: RWI_TP_BIOS0013 Revision 1

Reference: RWI_WI_BIOS0015

Effective Date: 15Jun2018

- If the day is missing, it will be imputed to the 15th day of the month.
- If both day and month are missing and the year is prior to the year of the signed ICF date, the month and day will be imputed as July 1st.
- If both day and month are missing and the year is the same as the year of the signed ICF date, the month and day will be imputed as January 1st.
- If the date is completely missing, no imputation will be performed.

Exposure:

Incomplete and partial dates for date of first use of re-usable Respimat® SMI prior to study entry will be imputed as follows:

- If the day is missing, it will be imputed to the 15th day of the month.
- If both day and month are missing and the year is prior to the year of the signed ICF date, the month and day will be imputed as July 1st.
- If both day and month are missing and the year is the same as the year of the signed ICF date, the month and day will be imputed as January 1st.

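### SAP 16 puts a long-term medication that was stopped in the 6 months before entry in neither the previous nor the concomitant class

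*SAP*

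**What the plan says.** SAP 16 has two classes and no third.

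- **Concomitant.** "Concomitant medications are medications which started prior to the study entry (date of signed ICF) and continued during the study period", together with medications begun during the study period. There is one catch-all: "Any medication without the start and end date will also be considered as concomitant".
- **Previous.** "Previous medications are those medications which were started and stopped in the 6 months prior to study entry".

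The output is a frequency table: "Previous and concomitant medications will be summarised as the number and percentage of patients by PT", overall and by cohort, split by COPD-related status.

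The protocol's covariate list (9.3.3) describes the data as "COPD-related and other concomitant medications, based on medical prescription history, in the 6 months prior to study entry and during the study period". The visit tables in both documents use the same 6-month window. SAP 4.3 records no change of analysis or definition from the protocol.

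SAP 18 draws on the same eCRF medication pages: "Information on previous non-Respimat® maintenance product use in the 6 months prior to study entry will be collected". Its rule for the last product before entry takes the product "prescribed prior to study entry where max (Start date) < date of signed ICF and End date < date of signed ICF", with no lower limit on the start date.

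**The concern.** The protocol's window concerns medication taken in the 6 months before entry. The SAP 16 sentence requires the start as well as the stop to fall in that window. A drug taken for years and stopped a few weeks before the visit fails the first condition, and because it was stopped it also fails the concomitant definition. A short course begun and ended in the window is counted.

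The omission is therefore systematic: it removes long-standing treatment that was stopped and keeps brief treatment. The tables show counts and percentages by preferred term, so their reader has no sign that anything is missing. For maintenance inhalers, the same report would show the product under SAP 18 and not under SAP 16.

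**Working it through.** There is no stated figure to reproduce. The check applies the written date rules to example medications.

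**Inputs.** Illustrative signed ICF date 15 Oct 2019, inside the planned enrolment period. The 6-month window then runs from 15 Apr to 14 Oct 2019, which is 16 + 31 + 30 + 31 + 31 + 30 + 14 = 183 days.

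**Rules, with S = start and E = stop.**

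- Concomitant (SAP 16): S before ICF and still taken in the study period, or S during the study period, or both dates absent.
- Previous (SAP 16, as written): S on or after 15 Apr 2019 and E before ICF.
- Previous (proposed): E from 15 Apr 2019 up to the day before ICF, any S.

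| Start | Stop | Days of window covered | SAP 16 as written | Proposed |
|---|---|---|---|---|
| 1 Oct 2016 | 1 Oct 2019 | 170 | neither | previous |
| 1 Oct 2016 | 14 Oct 2019 | 183 | neither | previous |
| 15 Mar 2019 | 15 Sep 2019 | 154 | neither | previous |
| 15 May 2019 | 15 Sep 2019 | 124 | previous | previous |
| 1 Oct 2016 | ongoing | 183 | concomitant | concomitant |
| 1 Oct 2016 | 15 Oct 2019 (ICF date) | 183 | concomitant, if the ICF date belongs to the study period | concomitant |
| 1 Oct 2016 | 15 Feb 2019 | 0 | neither | neither |

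The second row was taken on all 183 days and is unclassified, while the fourth was taken on 124 days (17 + 30 + 31 + 31 + 15) and is counted. The proposed rule recovers the three lost cases, leaves the ongoing drug where it was, and still excludes the drug that ended before the window opened.

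**Does anything else in the SAP close the gap?**

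- The catch-all covers only medications lacking both dates, so a dated drug is not rescued.
- Appendix 2 sets a wholly missing start to the signed ICF date. For a drug stopped earlier, the imputed start then falls after the stop, which does not place it properly in either class.

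**What remains visible elsewhere.** If the drugs in the first three rows are non-Respimat maintenance inhalers, SAP 18 still reports them. SAP 17 reports prior Respimat use, with no 6-month limit on its start. SAP 18 is restricted to COPD inhalers given for maintenance, so relievers, oral COPD drugs and non-COPD drugs have no second table.

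**Stop on the ICF date.** SAP 8.4 makes the baseline visit the visit at which the ICF is signed, and footnote 4 of SAP Table 1 starts the study period at that visit. A drug taken up to that date therefore reaches the study period, but SAP 16 does not say so.

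**The case against.** The strongest reply is that the sentence is loose drafting. The authors may have meant the 6 months to qualify only the stop, which would agree with the protocol and with the declaration of no changes in SAP 4.3. That is plausible, but the sentence does not say it, and two programmers could produce different tables from it. A supportive listing is also planned; it may show the drugs, but it does not repair the counts.

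Three stronger readings are tempting, and the documents do not support them.

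- **A reader might infer that naive patients would look much less pre-treated overall.** Their prior maintenance inhalers are reported in SAP 18 by product, class, duration and device. The disposition table in SAP 11 counts patients with any such product, and SAP 9.4 uses the last product and last device as subgroups. An inhaler replaced at the baseline visit may also be stopped on or after that day, and can then count as concomitant.
- **A reader might infer that partial-date imputation widens the gap,** because Appendix 2 says "In all other cases, the missing medication day or missing medication month will be replaced by 1". Enrolment runs from August (protocol) or September (SAP) to December 2019, so the window opens in February 2019 at the earliest, and a start known only as 2018 is outside it whatever month is imputed. A start known only as 2019 is set to the ICF date instead. The rule can move a start across the boundary only when the month is known and is the month in which the window opens.
- **A reader might take half of the planned 250, that is 250 × 0.5 = 125, as the number affected.** That is only a ceiling on the naive cohort, since at least half of the patients are expected to be experienced. It includes patients with no prior drug, with ongoing treatment, or with a stop at or after baseline.

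**Conclusion.** The gap is real in the written rule. A dated medication begun more than 6 months before entry and stopped within those 6 months, before the signed ICF date, is counted in neither SAP 16 class, although the protocol's window includes it.

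Its reach is limited to the descriptive SAP 16 tables. The loss is fullest for stopped long-term relievers, oral COPD drugs and non-COPD drugs. For maintenance inhalers the result is a disagreement between SAP 16 and SAP 18, not a disappearance from the report. The previous/concomitant classification enters no primary or secondary outcome, so the PASAPQ results are untouched. The documents give no basis for estimating how many patients or drugs are affected.

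The conclusion rests on a literal reading of the definition. If the authors intended the 6 months to apply to the stop alone, the point becomes a wording correction, and the change needed is the same.

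**What to change.** In SAP 16, define a previous medication as any medication whose stop date falls before the signed ICF date and within the 6 months before it, regardless of the start date, whether recorded or imputed. Keep the concomitant definition, and add that a medication stopped on the signed ICF date counts as concomitant because the study period starts at the baseline visit.

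The two classes then cover every medication with a known stop date in the protocol's window and agree with SAP 18 on maintenance inhalers stopped in that window. The cost is a sentence or two in the SAP and one condition in the derivation program. No new data are needed, and the change can be made before database lock.
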